### 6.6.2 Laboratory Test

Laboratory parameters for emergency immunization schedule and routine immunization schedule in Phase I will be analyzed in the following way.

Laboratory parameters at each time point and change from baseline to each post-baseline time point will be summarized using descriptive summary statistics for each parameter by group, and ANOVA will be used to detect the difference among groups. Group t-test will be used to detect the difference between immunization schedules by group.

Additionally, the counts and frequency of laboratory clinical significances will be calculated for each parameter and visit by group. Fisher exact test will be used to detect the difference for each parameter and visit among groups. Shift Tables from pre-vaccination to post-vaccination will be provided for each laboratory parameter by the group.

Also, the occurrence of clinically significant abnormal laboratory results within a trial subject will be analyzed using descriptive summary statistics for each parameter and visit by group.

### 6.6.3 Antinuclear Antibody

(1) The statistical method for antinuclear antibody evaluation for emergency immunization schedule and routine immunization schedule in Phase I will be carried out as follows.

The positive rate of antinuclear antibody was calculated by group on the 7th day after the first dose of immunization in phase I emergency immunization schedule, and their confidence intervals will be estimated by the Clopper-Pearson method. A Chi-square test or Fisher exact test will be used to detect differences among groups. Furthermore, if statistically significance exists, the pairwise comparison will be conducted between groups by Chi-square test or Fisher exact test.

Descriptive statistics in each group for the antinuclear antibody geometric mean titers (GMTs) and geometric mean increasements (GMIs) at 7th day after the first dose of immunization in phase I emergency immunization schedule, including geometric mean and 95% confidence interval (95% CI), will be provided by group. ANOVA model with log-transformation (per GMT and GMI as above) will be used to detect the difference among groups.

The statistical analysis method of antinuclear antibody evaluation on 14, 21, 28, 42 days after the first dose immunization of phase I emergency immunization schedule and 28, 35, 42, 56 days after the first dose immunization of phase I routine immunization schedule was the same as that of 7 days after the first dose in emergency immunization schedule of phase I.

Additionally, using the same method, the positive rate of antinuclear antibody comparison between emergency immunization schedule and routine immunization schedule in Phase I will be conducted by group (medium-dose group and high-dose group) at 14 days and 28 days after the whole schedule vaccination, respectively. 14 days after the whole schedule vaccination is 28 days after their first dose in emergency immunization schedule and 42 days after the first dose in routine immunization schedule, respectively. Meanwhile, 28 days after the whole schedule vaccination is 42 days after their first dose in emergency immunization schedule and 56 days after the first dose in routine immunization schedule, respectively.

(2) The statistical method for antinuclear antibody evaluation for emergency immunization schedule and routine immunization schedule in Phase II will be carried out as follows.

The positive rate of antinuclear antibody was calculated by group on the 28th day after the first dose of immunization in phase II emergency immunization schedule, and their confidence intervals will be estimated by the Clopper-Pearson method. A Chi-square test or Fisher exact test will be used to detect differences among groups. Furthermore, if statistically significance exists, the pairwise comparison will be conducted between groups by Chi-square test or Fisher exact test.

Descriptive statistics in each group for the antinuclear antibody geometric mean titers (GMTs) and geometric mean increases (GMIs) at 7th day after the first dose of immunization in phase II emergency immunization schedule, including geometric mean and 95% confidence interval (95% CI), will be provided by group. ANOVA model with log-transformation (per GMT and GMI as above) will be used to detect the difference among groups.

The statistical analysis method of antinuclear antibody evaluation on 42 days after the first dose immunization of phase II emergency immunization schedule and 56 days after the first dose immunization of phase II routine immunization schedule was the same as that of 28 days after the first dose in emergency immunization schedule of phase II.

Chi-square test or Fisher exact test will be used to detect differences of positive rate of antinuclear antibody between the middle dose group and the high-dose group at 28 days after the whole immunization in phase II. Additionally, using the same method, the positive rate of antinuclear antibody comparison between emergency immunization schedule and routine immunization schedule in Phase II will be conducted by group (medium-dose group and high-dose group) at 14 days and 28 days after the whole schedule vaccination, respectively. 14 days after the whole schedule vaccination is 28 days after their first dose in emergency immunization schedule and 42 days after the first dose in routine immunization schedule, respectively.

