## 3. Design

### 3.1 Overall Design

Single centered, randomized, double-blinded, and placebo-controlled clinical trial design is adopted.

A total of 144 healthy adults aged 18~59 years old are selected as subjects in phase I. After informed consent, subjects who pass the physical examination, meet the inclusion criteria and did not meet the exclusion criteria will be enrolled into the study. The subjects for the emergency immunization schedule (day 0, 14) and routine immunization schedule (day 0, 28) respectively, with 72 subjects for each immunization schedule. Simultaneously, subjects are phased enrolled, with 36 at medium dosage stage which will run-in first, following by 36 at high dosage stage. The subjects enrolled in each dosage stage will be randomly assigned in a 2:1 ratio to receive vaccine or placebo. The high dosage stage vaccination will start only with the condition that safety observation 0~7 days after the first dose of the medium dosage stage vaccination is finished, and the good safety profiles are confirmed by the DMC, according to the occurrence of the solicited and unsolicited adverse events, as well as the occurrence of the abnormal results of the blood routine, blood biochemistry, and urine routine testing.

The phase II clinical trial will start only with the condition that safety observation 0~7 days after the first dose of the high dosage stage vaccination is finished, and the good safety profiles are confirmed by the DMC. A total of 600 healthy adults aged 18~59 years old are selected as subjects. After informed consent, subjects who pass the physical examination, meet the inclusion criteria and didn't meet the exclusion criteria will be enrolled into the study. Subjects will receive two doses of injection at the emergency immunization schedule of day 0,14 or routine immunization schedule of day 0,28, with 300 subjects for each immunization schedule. The subjects for each schedule will be

randomly assigned in a 2:2:1 ratio to receive the medium dosage, high dosage vaccine, or placebo.

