### 3.3 Sample Size

**Clinical trial phase I:** According to the requirements of the *Good Clinical Practice* and *Provisions for Drug Registration*, phase I clinical trial is a small size study aims to safety evaluation. The total sample size of phase I are 144 subjects, with a total of 72 subjects for each immunization schedule, and 48 subjects receive medium or high dosage investigational vaccine for each immunization schedule. The sample size meets the requirements of the phase I clinical trial.

**Clinical trial phase II:** According to the requirements of the *Good Clinical Practice* and *Provisions for Drug Registration*, the phase II clinical trial mainly evaluates the immunogenicity and safety of different dosage vaccine in the targeted subjects and the sample size is more than 300. The total number of subjects in phase II is 600, with that of subjects receive medium, high dosage vaccine and placebo as 240, 240, and 120 respectively. Thus, the subjects in the trial group are 480. The sample size meets the requirement of phase II clinical trial.

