#### 4.2.3 Safety Endpoint

The safety endpoints of emergency immunization schedule and routine immunization schedule were as follows:

- (1) Adverse events includes:
  - Solicited adverse events: the systemic adverse events and local adverse events actively collected during the solicitation period (within 0-7 days after each dose of vaccination). Systemic adverse events include fever (axillary), acute allergic reaction, skin and mucosa abnormality, diarrhea, anorexia, vomiting, nausea, muscle pain, headache, cough, fatigue; local adverse events includes pain, induration, swelling, redness, rash, and pruritus.
  - Unsolicited adverse events: Including other adverse events in the solicitation period and all adverse events in the unsolicitation period.
- (2) Serious adverse event (SAE);
- (3) Antinuclear antibody: The positive rates at 28, 42 days after the first dose of vaccination (emergency immunization schedule), and 56 days after the first dose of vaccination (routine immunization schedule). Positive was defined as antinuclear antibody concentration  $\geq 10\text{U/ml}$ .

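### The added Phase II antinuclear-antibody comparison names only medium v high dose and leaves pooling over schedules unstated; vaccine v placebo is compared only within schedule, with no interval for the difference

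*SAP*

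**What the plan says.** ANA positivity is a Phase II safety endpoint. Section 4.2.3 defines it as "The positive rates at 28, 42 days after the first dose of vaccination (emergency immunization schedule), and 56 days after the first dose" in the routine schedule.

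Section 6.6.3, part (2), sets out the analysis in three layers:

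- **Within schedule.** Positive rates by group with Clopper-Pearson intervals, then "A Chi-square test or Fisher exact test will be used to detect differences among groups". Pairwise tests are conditional: "if statistically significance exists, the pairwise comparison will be conducted between groups by Chi-square test or Fisher exact test". Geometric means with 95% CIs and a log-scale ANOVA among groups are also planned. The method covers emergency days 28 and 42 and routine day 56.
- **Dose contrast.** A further chi-square or Fisher test of positive rates "between the middle dose group and the high-dose group at 28 days after the whole immunization in phase II". It carries no condition and names neither placebo nor a schedule.
- **Schedule contrast.** Emergency v routine, for the medium and high dose groups only.

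Group sizes come from sections 3.1 and 3.3. Phase II has two schedules, "with 300 subjects for each immunization schedule", and within each schedule subjects are "randomly assigned in a 2:2:1 ratio to receive the medium dosage, high dosage vaccine, or placebo".

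**The concern.** For a safety marker such as ANA, the main question is whether vaccinated subjects become positive more often than placebo subjects. A medium v high test cannot answer it: if both doses raise ANA equally, the expected difference is zero.

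The order of the tests also looks reversed. The dose contrast is unconditional, whereas each pairwise vaccine v placebo rate test must first pass a three-group test in a schedule with only 60 placebo subjects. Placebo samples at the same visit exist in both schedules, but no analysis combines them, and no confidence interval for a vaccine-placebo rate difference is specified anywhere in 6.6.3. What is at stake is how tightly the trial can bound an excess of ANA positivity from samples it already collects.

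**Working it through.** **1. Group sizes.** 300 per schedule at 2:2:1 gives 300 × 2/5 = 120 medium, 120 high and 300 × 1/5 = 60 placebo. Two schedules give 240, 240 and 120. This reproduces section 3.3: "subjects receive medium, high dosage vaccine and placebo as 240, 240, and 120 respectively", and "Thus, the subjects in the trial group are 480" (240 + 240).

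**2. Same visit.** Doses are given on days 0 and 14 or days 0 and 28, so 28 days after the full course is day 14 + 28 = 42 (emergency) or 28 + 28 = 56 (routine). Placebo is therefore already in the three-group tests at the visit used for the added contrast.

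**3. Effective size per arm**, 2 / (1/n₁ + 1/n₂):

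| Contrast | n | Effective n per arm | Named in 6.6.3(2)? |
|---|---|---|---|
| One dose v placebo, one schedule | 120 v 60 | 80 | Yes, after the three-group test |
| Medium v high, one schedule | 120 v 120 | 120 | Yes |
| Medium v high, both schedules | 240 v 240 | 240 | Only if the added contrast is pooled |
| One dose v placebo, both schedules | 240 v 120 | 160 | No |
| Both doses v placebo, both schedules | 480 v 120 | 192 | No |

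**4. Power.** The SAP gives no ANA rates, test level or sidedness. Assumed here: two-sided 5%, both doses with the same rate, the same rates in both schedules. Power is by exact enumeration of binomial outcomes; the lower figure is Fisher and the upper is uncorrected chi-square. The combined figures use crude pooling, a close stand-in for a stratified test when rates do not differ by schedule.

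| Placebo v vaccine rate | 120 v 60 | 240 v 120 | 480 v 120 |
|---|---|---|---|
| 3% v 8% | 16-21% | 42-45% | 48-50% |
| 5% v 12% | 25-32% | 56-59% | 64-65% |

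At 3% v 8%, the planned sequence in one schedule (three-group chi-square, then pairwise Fisher) finds either dose different from placebo in about 13% of 4000 simulated trials.

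A normal-approximation calculation over four other assumed pairs (2% v 7%, 5% v 10%, 5% v 15%, 10% v 20%) points the same way: 18-51% for one dose v placebo in one schedule, 35-84% for one dose over both schedules, and 38-90% for both doses over both schedules.

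**5. Precision at 3% v 8%.** Half-width = 1.96 × √(0.03 × 0.97/n_placebo + 0.08 × 0.92/n_vaccine).

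- 120 v 60: 1.96 × √(0.000485 + 0.000613) = 6.5 points
- 240 v 120: 1.96 × √(0.000243 + 0.000307) = 4.6 points
- 480 v 120: 1.96 × √(0.000243 + 0.000153) = 3.9 points

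The like-for-like gain from combining schedules is 6.5 to 4.6. The further step to 3.9 comes from also merging the doses. With about 60 × 0.03 = 1.8 expected placebo positives per schedule, the normal approximation is rough, so these widths are a guide only.

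**The case against.** The strongest reply is that the placebo question is already asked. At days 42 and 56 the plan compares all three groups on positive rates, with intervals by group, and on geometric means by ANOVA. The ANOVA does not depend on the 10 U/ml cut-off, so the power figures above do not describe all the planned evidence. This stands. A reader might infer from the added sentence that vaccine v placebo goes untested at this visit; the SAP does not support that.

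A reader might also infer that medium v high is the best-powered ANA contrast in the plan. That holds only if the sentence pools the schedules (240 v 240), which the SAP never says. Read per schedule, it repeats a pair already covered by the conditional pairwise step, though without the condition. Nor does the timing force pooling: Table 1 schedules Phase II ANA samples in both schedules at baseline and at 6 months as well.

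Three further points have weight:

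- By-schedule analysis is the plan's general design, and choosing a dose is a stated Phase II aim (section 2.2), so a dose contrast is legitimate.
- Section 6.7 makes every p-value nominal, so a null dose contrast could not stand as formal reassurance.
- The single-schedule power understates a plan that tests two schedules. Taking 13% in each, the chance of a finding in at least one is 1 − 0.87² = 24%. The proposed analysis is itself only moderately powered for a small excess.

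What remains is narrower. The sentence is ambiguous, and the more precise vaccine-placebo estimate that the data allow is not planned. Nominal p-values make that estimate and its interval more useful.

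**Conclusion.** The point holds in limited form. The added Phase II ANA contrast leaves out placebo and does not state its population. The planned vaccine v placebo rate comparisons are within schedule, at 120 v 60, with pairwise tests only after a significant three-group test and no interval for the difference.

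Combining schedules would raise power for one dose v placebo from 16-21% to 42-45% at 3% v 8%, and narrow the 95% CI half-width by 6.5 − 4.6 = 1.9 points. The absolute figures rest on assumed rates. The direction does not, provided the vaccine-placebo difference is similar in the two schedules, because the effective size per arm doubles from 80 to 160.

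Severity is low: the study is exploratory, p-values are nominal, and rates with intervals are already reported by group.

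**What to change.** In section 6.6.3, part (2):

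1. State whether the medium v high comparison 28 days after the full course combines the two schedules.
2. Add, from day 42 (emergency) and day 56 (routine), a comparison of each dose and of both doses combined with placebo, stratified by schedule. Use a Cochran-Mantel-Haenszel or exact stratified test, and report the stratified rate difference with its 95% CI.
3. Keep medium v high and the by-schedule tables.

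The cost is SAP wording and one extra exploratory table from samples already scheduled, with no added subjects or procedures. The downside is that the combined estimate averages over two schedules whose effects may differ, so it should be read beside the by-schedule results.

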#### **6.6.4 Inflammatory Factors**

The statistical method for inflammatory factors evaluation for emergency immunization schedule and routine immunization schedule in Phase I will be carried out as follows.

The changes of IL-6, IL-2, and TNF- $\alpha$  comparison between emergency immunization schedule and routine immunization schedule will be conducted by group (medium-dose group, high-dose group and placebo group) at 7 days after each dose were statistically described, and the difference among groups was analyzed by Rank-sum test.

#### **6.7 Multiplicity problem**

This study is a phase I / II exploratory study, so multiple adjustments are not considered. In the results of immunogenicity evaluation and safety evaluation, the calculated p-value is only nominal p-value, which is mainly used to describe the strength of association between evaluation endpoint and treatment group, but not as the basis for formal statistical inference.

#### **6.8 Subgroup analysis**

Subgroup analysis was not planned for this trial.

#### **6.9 Processing of missing data**

Concerning the statistical analysis of FAS, the missing data of the post-vaccination antibody test result will be filled

by the method of Last Observation Carried Forward (LOCF). The missing data of the pre-vaccination antibody result will be filled with the maximum of pre-vaccination antibody results among all the subjects. In terms of the evaluation of the immunogenicity, exploratory, and safety endpoints, missing data will not be filled.

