**Table 2 Blood collection at different time points in immunogenicity observation**

Phase and immunization schedule	Test contents	Sampling time
Phase I - emergency immunization schedule	Neutralizing antibody, IgG, IgM	Before the first dose of inoculation (D0), 7 days after the first dose of inoculation (D7), 14 days after the first dose of inoculation (D14), 21 days after the first dose of inoculation (D21), 28 days after the first dose of inoculation (D28), 42 days after the first dose of inoculation (D42), 6 months after the whole schedule vaccination (D194)
	T cell response	Before the first dose of inoculation (D0), 14 days after the first dose of inoculation (D14), 14 days after the whole schedule vaccination (D28)
Phase I - routine immunization schedule	Neutralizing antibody, IgG, IgM	Before the first dose of inoculation (D0), 28 days after the first dose of inoculation (D28), 35 days after the first dose of inoculation (D35), 42 days after the first dose of inoculation (D42), 56 days after the first dose of inoculation (D56), 6 months after the whole schedule vaccination (D208)
	T cell response	Before the first dose of inoculation (D0), 28 days after the first dose of inoculation (D28), 42 days after the first dose of inoculation (D42)
Phase II - emergency immunization schedule	Neutralizing antibody	Before the first dose of inoculation (D0), 14 days after the whole schedule vaccination (D28), 42 days after the first dose of inoculation (D42), 6 months after the whole schedule vaccination (D194)
Phase II - routine immunization schedule	Neutralizing antibody	Before the first dose of inoculation (D0), 28 days after the whole schedule vaccination (D56), 6 months after the whole schedule vaccination (D208)

This study was carried out by the Jiangsu Provincial Center for Disease Control and Prevention (Public Health Research Institute of Jiangsu Province).

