### 5. Analysis Set

**Full Analysis Set (FAS):** A subjects defined according to the principle of intent analysis (ITT), including all the subjects who have been randomized, have received at least one dose of vaccination, have finished blood collection before/after vaccination for at least one time with the corresponding antibody assay results provided. The subjects who are vaccinated with the wrong vaccine will be kept in the originally assigned group according to the ITT principle, for the immunogenicity evaluation.

**Per-Protocol Set (PPS):** A subset of FAS, including all the subjects who meet the inclusion criteria and don't meet the exclusion criteria, have been randomized, have finished the full-course vaccination within the protocol required time window, and have finished the blood collection before/after vaccination with the corresponding antibody assay results provided. Subjects who meet the following conditions are not allowed to enter PPS:

- (1) Those who violate the test scheme;
- (2) Those who are vaccinated with the wrong vaccine;
- (3) Use of protocol prohibited vaccines or drugs:
  - Other investigational or unlicensed products (drugs or vaccines)
  - long-term use (lasting more than 14 days) of immunosuppressive or other immunomodulatory drugs (inhaled or topical steroids are allowed)

- Immunoglobulin and/or blood preparations
- (4) Newly diagnosed autoimmune diseases, including human immunodeficiency virus (HIV) infection;
- (5) Other situations affecting the evaluation of vaccine immunogenicity.

**Immune Persistence Set (IPS):** All subjects who had completed the whole schedule vaccination and had effective antibody titer value at 6 months after the whole schedule vaccination were included.

The above Full Analysis Set, Per-Protocol Set, and Immune Persistence Set are defined for emergency immunization schedule and routine immunization schedule in phases I and II.

**Safety Analysis Set (Safety Set, SS):** All randomized subjects with at least one dose of the study vaccine were included. Among them, according to ASaT (All Subjects as Treated) principle, the safety evaluation was carried out according to the actual vaccination group.

- The safety set is mainly used for the safety evaluation of the vaccine, and the safety set of each dose is used for the safety evaluation of each dose.

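### Section 6.9 both fills and does not fill missing antibody titres, and at the Phase II primary time points LOCF has only the pre-vaccination titre to carry, or nothing

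*SAP*

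**What the plan says.** Section 6.9 holds three statements on missing data:

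- After vaccination: "Concerning the statistical analysis of FAS, the missing data of the post-vaccination antibody test result will be filled", with LOCF as the method.
- Before vaccination: "The missing data of the pre-vaccination antibody result will be filled with the maximum of pre-vaccination antibody results among all the subjects".
- In general: "In terms of the evaluation of the immunogenicity, exploratory, and safety endpoints, missing data will not be filled".

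The third statement is not limited to any analysis set. Section 5 makes the FAS an immunogenicity set: wrongly vaccinated subjects "will be kept in the originally assigned group according to the ITT principle, for the immunogenicity evaluation". To enter the FAS, a subject must "have finished blood collection before/after vaccination for at least one time with the corresponding antibody assay results provided".

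Section 4.2.1.1 sets the Phase II primary endpoints (seroconversion rate-1 and rate-2) at 14 days after the second dose for the emergency schedule and at 28 days after it for the routine schedule. Table 2 gives Phase II neutralizing-antibody sampling at D0, D28, D42 and D194 for the emergency schedule. For the routine schedule it reads "Before the first dose of inoculation (D0), 28 days after the whole schedule vaccination (D56), 6 months after the whole schedule vaccination (D208").

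**The concern.** Neutralizing titres are the immunogenicity endpoints, so the filling rules and the no-filling rule in Section 6.9 apply to the same FAS data. Two programmers could follow the section faithfully and report different FAS seroconversion rates, GMTs and GMIs.

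The filling rule has its own fault. LOCF assumes that the last value is a fair stand-in for the missing one. Before D28 or D56 in Phase II the last value, if any is carried, is from before vaccination. The subject is then analysed as vaccinated but unresponsive, although the response was simply not measured.

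Section 2.2 says that Phase II is to settle dosage and schedule for further evaluation. A rule that moves the estimates in proportion to missed blood draws, and not equally across schedules, bears on that choice. Section 7 also allows slight changes of method in the light of the final data, so the choice between the two rules could be made after results are seen.

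**Working it through.** **1. The plan's own figure.** Section 3.1 puts 300 subjects in each Phase II schedule, allocated 2:2:1. That is 300 × 2/5 = 120, 300 × 2/5 = 120 and 300 × 1/5 = 60. Over two schedules this gives 240, 240 and 120, as stated in Section 3.3. Each vaccine arm within a schedule has n = 120. The SAP states no missing rate, response rate or titre level.

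**2. What LOCF can carry in Phase II (Table 2).**

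| Schedule | Time point | Study day | Earlier samples |
|---|---|---|---|
| Emergency | primary, 14 days after dose 2 | 14 + 14 = D28 | D0 |
| Routine | primary, 28 days after dose 2 | 28 + 28 = D56 | D0 |
| Emergency | secondary, 28 days after dose 2 | 14 + 28 = D42 | D0, D28 |

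**3. Effect on one subject if D0 is carried.** Post then equals pre. The first branch of the seroconversion definition (Section 4.1.1) needs a baseline below the threshold (1:4 or 1:8) and a later titre at or above it, which is impossible when the two are equal. The second branch needs at least a 4-fold rise, and the ratio is 1. So no filled subject can seroconvert at any baseline under either threshold, and each contributes a fold rise of 1 to the GMI.

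**4. Effect on an arm.** Let p be the rate and G the GMT among observed subjects, m the fraction filled, and B the GMT of the carried baselines.

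- Rate under LOCF = p(1 − m)
- GMT under LOCF = exp[(1 − m) ln G + m ln B]

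Assumptions, none from the SAP: p = 95%, G = 30, B = 2.

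- m = 5%: 0.95 × 0.95 = 90.3%; GMT = exp(0.95 × 3.401 + 0.05 × 0.693) = 26.2, down 13%.
- m = 10%: 0.95 × 0.90 = 85.5%; GMT = exp(0.90 × 3.401 + 0.10 × 0.693) = 22.9, down 24%.

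Over other assumed values: for p from 50% to 95% the loss p × m is 2.5 to 4.75 points at m = 5% and 5.0 to 9.5 points at m = 10%. For G from 8 to 64 the GMT is multiplied by 0.93 to 0.84 at m = 5% and by 0.87 to 0.71 at m = 10%.

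In counts, for one arm of 120 with 12 missing and 97 of the 108 observed converting: 97/108 = 89.8% without filling, 97/120 = 80.8% with D0 carried.

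**5. Effect on the schedule comparison.** Section 6.4 compares the schedules within each dose group in Phase II. Before six months, 28 days after the second dose is the only post-vaccination interval sampled in both schedules. A missing emergency D42 value can take the D28 post-vaccination titre; a missing routine D56 value can only take D0. As an illustration, let both schedules truly reach 95%, let 5% be missing in each, and let the emergency D28 values be present with 95% already converted. The emergency rate stays at 0.95 × 0.95 + 0.05 × 0.95 = 95%, while the routine rate becomes 0.95 × 0.95 = 90.3%. The gap of about 4.75 points comes only from the fill.

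**6. The baseline fill.** Giving a missing baseline the highest baseline of all subjects can only lower that subject's fold rise and chance of seroconverting, or leave them unchanged. It conflicts with the no-filling sentence just as LOCF does.

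**The case against.** The best defence is that the last sentence of Section 6.9 was meant for the sets other than the FAS, which would reconcile the rules. The text does not say so. That reading also leaves the sentence little to do for titres, since Section 5 already requires PPS subjects to have assay results and IPS subjects to have a six-month titre.

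Other points limit the finding, and these stand:

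- **Carrying D0 is not certain.** Section 6.9 treats pre- and post-vaccination results under separate rules. If only post-vaccination values may be carried, LOCF does nothing at D28 or D56. The SAP does not say which applies.
- **Few subjects may be filled.** If FAS entry requires a before-and-after pair, a subject missing D56 enters only with a D208 sample, and one missing D28 only with D42 or D194.
- **For the rates, carrying D0 equals counting missing as failure.** That is defensible as a labelled sensitivity analysis, but not as an unstated result of the main rule. The same defence is not available for GMT and GMI.
- **The study is exploratory.** Section 6.7 makes p-values nominal. This does not help, because the estimates themselves change.

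A reader might infer more than the document supports:

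- *That the primary result depends on which sentence is followed.* LOCF is tied to the FAS, and the SAP does not say whether the FAS or the PPS leads. If the PPS leads, LOCF does not touch the primary result.
- *That filling makes the confidence intervals too narrow.* In this scenario they widen: the Clopper-Pearson width is 9.1 points for 108/114 and 11.5 for 108/120. The fault is where the interval is centred.
- *That only the vaccine arms are affected.* The rule applies to all arms. The pull is mainly in the vaccine arms because placebo conversion is presumably near zero.
- *That Phase I LOCF always takes a value from the rising part of the response.* In the Phase I routine schedule nothing is sampled between D0 and D28, so a missing D28 would take D0.

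**Conclusion.** The point holds. Section 6.9 gives opposite instructions for missing FAS titres. Its LOCF rule at the Phase II primary time points either scores unmeasured subjects as non-responders or cannot operate.

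If D0 is carried, the FAS rate falls by the factor (1 − m) and the GMT moves toward baseline, mainly in the vaccine arms: about 5 to 10 points and 13% to 24% for 5% to 10% missing, under the assumed 95% conversion, GMT 30 and floor of 2. The formulas follow from the definitions and Table 2; the inputs are assumptions, and the true size cannot be fixed from the SAP. The distortion of the schedule comparison is possible, not established, and depends on how many draws are missed. The claim concerns FAS estimates. It becomes a claim about the primary result only if the FAS is the leading set.

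**What to change.** In Section 6.9, before database lock:

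- Delete both fill sentences, the LOCF one and the maximum-baseline one. Removing LOCF alone would leave a contradiction.
- Keep the no-filling rule and analyse observed titres at each time point. Seroconversion and GMI then also need an observed baseline.
- State that a pre-vaccination titre is never used as a post-vaccination result.
- Add a labelled FAS sensitivity analysis that counts missing as non-seroconverted for the rates. Multiple imputation of log titre for GMT and GMI is optional.

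The cost is SAP wording, one sensitivity table and slightly smaller denominators at each visit. Observed-titre results still assume that missed draws are unrelated to response; the sensitivity analysis shows how far the rates could fall if they are not.
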